## Abstract

The purpose of this SPiRE is to identify the supports and barriers to scalability of Veteran-tailored iTBS and APT across neurologic conditions, with the longer-term goal of providing an empirical basis for the tailoring of a broader range of cognitive rehabilitation strategies to optimize each Veteran's cognitive function in daily life. After Veterans receive standard cognitive rehabilitation, cognitive impairments often persist and if they do make gains there is limited carry-over to daily function. The tenets of precision neurorehabilitation suggest that tailored interventions will optimize gains and carry-over, but precision-tailoring of cognitive rehabilitation will only be possible if researchers develop and test scalable approaches for identifying, organizing, and analyzing the multitude of Veteran-specific variables driving and influencing treatment responsiveness. This project addresses long-standing scientific barriers to understanding treatment responsiveness, particularly study sample heterogeneity and individual variability. We address study sample heterogeneity by linking Veterans, across TBI and ischemic stroke, according to levels of cognitive impairment. We create a cohort of Veterans with a homogeneous level of cognitive impairment, thereby enabling explication of person-centric factors influencing treatment responsiveness and carry-over to daily function. Advancing understanding of the basic study design elements will be achieved by leveraging our knowledge of intermittent Theta Burst Stimulation (iTBS) and iTBS paired with Attention Processing Training exercises (iTBS + APT). iTBS is advantageous as it robustly improves working memory with just one treatment session. These interventions, together, are advantageous as they can each be tailored to a Veteran's unique cognitive challenges and to target the neural site, unique to each Veteran's neuropathology. These two interventions also directly address cognitive deficits, while simultaneously inducing neuroplasticity in neural regions hampered or impaired by neural injury. We will study Veterans with moderately impaired cognition who, after standard cognitive rehabilitation, continue to struggle with daily life requiring assistance with complex instrumental activities of daily living (IADL). Veterans will participate in a series of two within-subject treatment studies, conducted on two separate days, 2-weeks apart. Veterans will be randomly assigned to first receive a single session of Active iTBS or Placebo iTBS and then they will receive APT paired with their assigned iTBS (Active iTBS + APT vs Placebo iTBS + APT). We will test if diagnosis moderates the effects of these interventions on both immediate and persisting change in cognition. For immediate effects, we use a novel testing battery and for persisting gains we use established and feasible neuropsychological tests as well as an established test of cognitive function during IADL. Results will be used to obtain pilot data and examine feasibility in terms of study attrition relative to Veteran fatigue, mood, and Veteran reports of suitability of key aspects of the study design. These findings will be used to develop a future merit within-subject cross-over study examining the overarching hypothesis that tailored iTBS and APT applied to a transdiagnostic sample and subsequently matched to a Veteran, according to a biotype algorithm, will result in better functional performance of Veteran-valued IADL.

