### 3.0 Objectives

**Aim 1: Elucidate merits of transdiagnostic sampling.** Within the two intervention groups (Group 1: n = 24, Active iTBS and Active iTBS + APT; Group 2: n = 24, Placebo iTBS and Placebo iTBS + APT), we expect that (1i) neurologic diagnosis (stroke, TBI) will not moderate the effect of Active iTBS or Active iTBS + APT on Maximum Cognitive Gain as assessed by the Modified Digit Span (MDS) and the Streamlined AMPS (AMPS).

**Aim 2: Obtain pilot data to inform estimation of treatment and practice effects.** We will gather pilot data regarding the magnitude and duration of treatment effects as well as MDS and AMPS practice effects. As we anticipate (2i) greater immediate gains in IADL performance (AMPS) after Active iTBS + APT when compared to Active iTBS alone, we will compare Maximum Cognitive Gains (MCG) on MDS with MCG on AMPS between the Active iTBS and Active iTBS + APT groups to determine if MCGs differ in magnitude. We will also determine if

Active iTBS + APT trend lines indicate an additive treatment effect of APT on MDS and/or AMPS. We also anticipate (2ii) some persisting treatment effects and to explicate these effects we will examine effects for Active iTBS and Active iTBS + APT in the short-term (post-pre-treatment), long-term (2 weeks after a session) and cumulatively across treatment sessions. Since the AMPS uses a unique task during each testing interval and MDS uses 1 of 6 alternate test forms, we will determine (2iii) presence and magnitude of practice effects by testing whether prior exposure to MDS or AMPS results in MDS or AMPS gains for Placebo iTBS.

**Aim 3: Explicate study attrition by perceived suitability of aspects the study design and the relationship between this perceived suitability and fatigue as well as mood.** We will test the ideas that (3i) Attrition rates do not differ by stroke and TBI groups, (3ii) Veterans across stroke and TBI have similar perceptions regarding suitability of the number and type of tests as well as number of study-days, and (3iii) perceived suitability is related to Veteran-reported fatigue and mood.

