**Figure 1. Four Step Screening Process: Summary of Exclusion Criteria by Steps**

For this within-subject placebo-controlled partially-blinded treatment protocol (Fig 2), we will enroll 48 medically stable Veterans with stabilized recovery trajectories after a stroke or a TBI and who have a homogeneous level of moderately impaired cognitive function persisting after standard rehabilitation.

An equal number of Veterans with stroke/TBI (24-stroke; 24-TBI) will be enrolled, but we will over-sample females (Figure 2). For each iTBS group to include an equal number of Veterans with stroke/TBI, Veterans will be randomly assigned by diagnostic groups, to receive Active iTBS or Placebo iTBS. To measure immediate effects (ImE), an equal number of Veterans with stroke/TBI within each iTBS group will be randomly assigned to be tested with the Modified Digit Span (MDS) or AMPS, three times at 30 min intervals. Persisting effects (PE) tests will be administered to all participants at five timepoints including prior to and after Active iTBS or Placebo iTBS and 2-weeks later prior to the 2nd intervention, where all Veterans receive APT paired with their assigned iTBS (Active iTBS + APT or Placebo iTBS + APT). The alternate ImE test is then administered three times at 30 min intervals, followed by re-administration of all PE tests. Two weeks later, all PE tests are administered a 5th time (B4). ImE and PE measures are used to define magnitude and duration of cognitive change. Randomization (SAS Proc Plan) will be managed by one un-blinded researcher who will not provide interventions or conduct testing.

**Figure 2. Study Design (ImE = Immediate Effects Tests; AMPS = AMPS or MDS = Modified Digit Span; PE = Persisting Effects Tests for all participants; Study Day-1: Obtain Covariates and Treatment preparation information; B0 = Pre-Study-Day-2; B1 = Post-Study-Day-2; After 2-Weeks B2 = Pre-Study-Day-3; B3 = Post-Study-Day-3; After 2-Weeks B4 = Study-Day 4)**

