For measuring immediate changes in cognitive function, we will use the aforementioned **AMPS**. For each of the *three administrations, in 30-min intervals*, a unique task will be randomly selected (without replacement) from the set of tasks developed during Step 4 (Fig 1). Thus, the same IADL is never repeated for the same Veteran.

**Persisting Effects (PE) Measures.** This battery includes the same five tests/sub-tests administered during screening (Fig 1, Step-4: AMPS, RBANS, WAIS-IV Digit Span, DKEFS subtests and BRIEF-A). As the BRIEF-A will be re-administered, the study Neuropsychologist will review BRIEF-A scores and, if there are compelling reasons, Veterans with scores suggesting atypical validity will be withdrawn. This battery also includes tests to measure change in mood: Columbia Suicide Severity Rating Scale (C-SSRS) *Beck Anxiety Inventory (BAI)*, and the *Posttraumatic Stress Disorder Checklist (PCL)*. To assess fatigue, we will use the Fatigue Severity Scale (FSS), which is a self-report measure of prior-week fatigue during nine activities and current fatigue. To measure behavioral features of agitation, we will use the *Agitated Behavioral Scale (ABS)*.

Table 2: Instrumentation: Testing Battery					
Immediate Outcome Effects (ImE)	Hrs/Admin	Aims	Variable Types	# Reps	
AMPS	1.5	1 & 2	Continuous (logit)	3	
Modified Digit Span (MDS)	0.2	1 & 2	Proportional (% correct)	3	
Persisting Effects Testing Battery (PE)	Hrs/Admin	Aims	Variable Types	# Reps	
Repeatable Battery for Assessment of Neuropsych Status (RBANS)	1.0	2	Continuous (normed score)	5	
Weschler Adult Intelligence Scale (WAIS-IV) Digit Span			Proportional (% correct)	5	
Delis-Kaplan Executive Functioning System (DKEFS): Color-Word			Continuous (normed score)	5	
Behavior Rating Inventory of Executive Function (BRIEF)			Continuous (normed score)	5	
AMPS	1.5	2	Continuous (logit)	5	
PTSD Checklist (PCL)	0.1	2 & 3	Mean # symptoms/ severity	5	
Columbia Suicide Severity Rating Scale (C-SSRS)	0.1	2 & 3	Raw score (Veteran rating)	5	
Beck Anxiety Inventory (BAI)	0.1	2 & 3	Raw score (Veteran rating)	5	
Agitated Behavior Scale (ABS)	0.1	2 & 3	Raw score (research clinician rating)	5	
Fatigue Severity Scale (FSS): Prior Week Daily Living Score	0.1	2 & 3	Raw score (Veteran rating)	5	
Fatigue Severity Scale (FSS) L VASF Current Fatigue Rating	0.1	2 & 3	Raw score (Veteran rating)	5	

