## 5.6 Data Analysis

**Sample Size to Estimate Effect Sizes.** Our total sample size of 48 participants is based on 80% power to detect an Effect Size (ES) of .90. For 80% power, sample size per group to detect a small ES (0.35) is 130, for a medium ES (0.60) it is 42 and to detect a large ES (0.90) it is 21 per group. To estimate a large ES of 0.90, 42 subjects are required to achieve 80% power. Thus, we plan for 48 participants and 12% attrition.

Published methods  will be used to examine the merits of transdiagnostic sampling (Aim 1i). Specifically, we will use MLM to determine if neurologic diagnosis (stroke, TBI) moderates the effects of the Active intervention (Group 1: n = 24, Active iTBS and Active iTBS + APT; Group 2: n = 24, Placebo iTBS and Placebo iTBS + APT) on Maximum Cognitive Gain (MCG) as measured with the MDS and the AMPS.

For Aim 2, we will inform estimates of effect sizes by testing the idea (2i) that MDS gains and AMPS gains differ for Active iTBS and Active iTBS + APT. As specified in Table 1, we will examine if gains differ in magnitude by computing the MCGs for each outcome (MDS and AMPS) by each intervention. For each outcome, we will compare the Average Active iTBS MCG with the Average Placebo iTBS MCG and the Average Active iTBS + APT MCG with the

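### The Abstract promises a test of whether diagnosis moderates persisting change, but no aim, analysis or Table 2 entry provides one, although the persisting-effects battery is given to all 48 Veterans

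*Combined protocol and SAP*

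**What the plan says.** - **Abstract.** The commitment is: "We will test if diagnosis moderates the effects of these interventions on both immediate and persisting change in cognition". The sentence after it ties persisting gains to neuropsychological tests and to a test of cognition during daily activities. Those are the PE battery of section 5.5, so persisting change cannot mean a later reading of the immediate-effects (ImE) tests.
- **3.0 Objectives, Aim 1.** The expectation is that "neurologic diagnosis (stroke, TBI) will not moderate the effect of Active iTBS or Active iTBS + APT on Maximum Cognitive Gain", assessed by MDS and AMPS.
- **5.6 Data Analysis, Aim 1.** The plan is that "we will use MLM to determine if neurologic diagnosis (stroke, TBI) moderates the effects of the Active intervention", again on MCG from MDS and AMPS. No PE measure is named and no model terms are listed.
- **5.5 Study Evaluations, Table 2.** The ImE rows serve Aims 1 and 2, for example "Modified Digit Span (MDS) 0.2 1 & 2". The PE cognitive rows and the PE AMPS serve Aim 2, for example "Repeatable Battery for Assessment of Neuropsych Status (RBANS) 1.0 2". The PE mood and fatigue rows serve Aims 2 and 3. No PE row serves Aim 1.
- **5.6, Aims 2ii and 3.** PE measures are compared between Active and Placebo by t-tests, with no diagnosis term. The stroke-versus-TBI comparisons in Aim 3 concern attrition and suitability ratings.
- **5.1 Study Design, text below the Figure 1 caption.** "An equal number of Veterans with stroke/TBI (24-stroke; 24-TBI) will be enrolled", and "Veterans will be randomly assigned by diagnostic groups, to receive Active iTBS or Placebo iTBS". Half of each cell takes MDS and half AMPS after the first session, and the two swap after the second. Everyone takes the PE battery at B0 to B4.

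**The concern.** Aim 1 carries the argument for transdiagnostic sampling. A reader of the Abstract expects it to be examined for persisting as well as immediate change. Under the plan as written, the statistician would finish every listed analysis and still have no estimate of how the persisting effect differs between stroke and TBI.

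The gap matters more because Aim 1 predicts a null. Support for no moderation can come only from an interval narrow enough to exclude a large interaction. The PE data bear on that question, cover every participant and include a value taken before stimulation, yet they carry no diagnosis term.

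**Working it through.** **1. The plan's own figure.** Section 5.6 gives 21 per group for an effect size of 0.90 at 80% power, 42 in total, and 48 with 12% attrition. Assuming two-sided alpha 0.05 (not stated for the sample size), the noncentral t calculation gives 21 per group (power 81%), and 42/(1 − 0.12) = 47.7, so 48. The figure reproduces, but it is for a two-group main effect and not for an interaction.

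**2. Cell sizes.**
- PE measures: 48/(2 diagnoses × 2 arms) = 12 per cell.
- One ImE outcome within one session: 48/(2 × 2 × 2 ImE tests) = 6 per cell.
- One ImE outcome pooled over both sessions: 12 per cell, with session, APT and test order mixed in. Section 5.6 does not say which applies.

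**3. Precision of the diagnosis-by-arm interaction.** For four equal cells of m Veterans, SE = SD × √(4/m), df = 4m − 4, and the 95% half-width is t(0.975, df) × SE. Power is for an interaction of 0.90 SD, two-sided 0.05.

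| Data | m | SE (SD) | 95% half-width (SD) | Power |
|---|---|---|---|---|
| One ImE outcome, one session | 6 | 0.816 | 1.70 | 18% |
| PE, all 48 | 12 | 0.577 | 1.16 | 33% |
| PE, 42 completers | 10.5 | 0.617 | 1.25 | 30% |

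The like-for-like reduction from 6 to 12 per cell is 1 − 1.16/1.70 = 32%. Reaching 80% power for 0.90 SD would take about 40 per cell, or 160 Veterans.

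**4. Adjustment for B0.** The documents give no correlation between B0 and later PE scores, so a range is assumed. The half-width is multiplied by √(1 − r²):
- r = 0.5: 1.16 × 0.866 = 1.01 SD
- r = 0.7: 1.16 × 0.714 = 0.83 SD
- r = 0.8: 1.16 × 0.600 = 0.70 SD

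Similar adjustment may be open to the ImE models. The PE battery given before the first stimulation includes AMPS, and it includes the WAIS-IV Digit Span on which MDS is based. At r = 0.7 the 6-per-cell half-width would be 1.70 × 0.714 = 1.21 SD, against 0.83 SD, which is again about 32%.

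**The case against.** The best reply is that Aim 1, its analysis paragraph and Table 2 agree with each other, and that a single Abstract sentence is out of line. Correcting that sentence would restore consistency. The added analysis would be weak (about 33% power unadjusted) and would bring several interaction estimates that the false-discovery rule, stated for Aims 2 and 3, does not cover. Working memory immediately after stimulation was also chosen for a reason: section 5.5 cites the largest effects there in healthy controls, while Aim 2 expects only some persisting effects.

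Much of this stands. Amending the Abstract is a legitimate way out, and the PE estimate would not settle Aim 1. But the Abstract sentence is explicit, the data will be collected anyway, and the estimate bears on the purpose of the pilot.

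Three stronger readings are tempting and are not supported:
- **That the PE data go unused.** They are used in Aims 2ii and 3, and only the diagnosis-moderation analysis is missing.
- **That Aim 1 certainly rests on 6 Veterans per cell.** This holds per outcome within one session. A mixed model pooling both sessions would have 12, and section 5.6 does not exclude it.
- **That the PE analysis would halve the interval.** Going from 1.70 to 0.83 SD credits an assumed correlation of 0.7 to the PE data alone. Treated alike, the reduction is about 32%, and it disappears if the ImE model pools sessions.

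**Conclusion.** The gap is real. The Abstract promises a moderation analysis of persisting change, and no aim, model or table entry delivers it. With 12 Veterans per cell, the missing interaction could be estimated to within ±1.16 SD unadjusted (±1.25 SD with 42 completers). With B0 adjustment this becomes about ±0.70 to ±1.01 SD for assumed correlations of 0.8 down to 0.5.

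These figures assume equal cells, two-sided 0.05 and a common SD. They are in SD units of whichever outcome is analysed, so the ImE and PE rows compare precision and not the same quantity.

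The gain should not be oversold. The unadjusted PE interval still admits an interaction larger than the 0.90 SD on which the trial was sized, and a non-significant result on either set of data must not be read as absence of moderation. The immediate-effect question also remains a separate one, which the PE data do not answer.

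**What to change.** - In section 5.6, add a diagnosis-by-arm (by-visit) term to B0-adjusted models of the PE cognitive measures: AMPS, RBANS, D-KEFS and WAIS-IV Digit Span. The B1 and B2 contrasts then concern iTBS alone, and B3 and B4 the two sessions together.
- Report the interaction estimates with 95% intervals as the persisting-change part of Aim 1, beside the ImE result. State that they are exploratory estimates and that non-significance is not evidence of no moderation.
- Extend Aim 1 in section 3.0 to match, and mark those PE rows of Table 2 as Aims 1 & 2.
- State in section 5.6 whether the Aim 1 mixed model is fitted within or across sessions, so that its cell size is known.
- If the sponsor does not intend this analysis, amend the Abstract sentence to immediate change only.

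The cost is a few model terms and a paragraph in the analysis section, with no new patients, visits or tests. The small downside is several extra estimates outside the false-discovery rule stated for Aims 2 and 3, which should be said when they are reported.

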
## List of Abbreviations

ABS: Agitated Behavioral Scale

AMPS: Assessment of Motor and Process Skills

APT: Attention Process Training

AUDIT-C: Alcohol Use Disorders Identification Test

BAI: Beck Anxiety Inventory

BRIEF-A: Behavior Rating Inventory of Executive Function

CDW: Corporate Data Warehouse

C-SSRS: Columbia Suicide Severity Rating Scale

CTI: Center for Translational Imaging

DAI: Diffuse Axonal Injury

DAST-10: Drug Abuse Screening Test

DLPFC: Dorsolateral Prefrontal Cortex

DKEFS: Delis-Kaplan Executive Function System

ES: Effect Size

FIM: Functional Independence Measure

fMRI: Functional Magnetic Resonance Imaging

FSS: Fatigue Severity Scale

GIMME: Group Iterative Multiple Model Estimation

IADLs: Instrumental Activities of Daily Living

ImE: Immediate Effects

iTBS: intermittent Theta Burst Stimulation

MCG: Maximum Cognitive Gains

MDS: Modified Digit Span Test

MLM: Mixed-Effects Linear Regression Model

MRI: Magnetic Resonance Imaging

NURIPS: Northwestern University Research Imaging Processing System

PCL: Posttraumatic Stress Disorder Checklist

PE: Persisting Effects

RBANS: Repeatable Battery for the Assessment of Neuropsychological Status

ROI: Region of Interest

TBI: Traumatic Brain Injury

WAIS-IV: Wechsler Adult Intelligence Scale Fourth Edition

## **2.0 Introduction**

Each year, 15,000 Veterans incur a new ischemic stroke (stroke) with many of the survivors (32% - 56%) experiencing persisting cognitive impairments  and continued cognitive degradation.  For the more than 40,000^3 service members with moderate to severe TBI, the rates are similar with about 65% experiencing long-term cognitive impairments.  Considering the high prevalence of persisting cognitive impairments and that standard stroke and TBI rehabilitation have limited impact in mitigating this fundamental barrier to daily function, this protocol tests the scalability of an approach to effectively and feasibly tailor iTBS and APT to a Veteran's level of cognitive impairment.

Considering that Veterans with the same neurologic diagnosis are not homogenous by brain pathology or recovery patterns  and further that Veteran-specific factors such as level of cognitive impairment influence recovery,  studying treatment responsiveness by diagnosis alone is unlikely to advance understanding of how to tailor interventions to maximize each Veteran's daily function. Thus, we apply our recent work  and ideas from the field of mental health  to pilot transdiagnostic sampling. More specifically, we create a sample of Veterans with either TBI or stroke who are linked across diagnoses by homogeneous levels of cognitive impairment. Applying our recent work,  we use the Functional Independence Measure (FIM) to broadly link Veterans according to the FIM category of moderate cognitive impairment. This category includes individuals with short-term memory problems requiring assistance for problem solving and shifting attention. As this is a broad link, we refine the link according to

neuropsychological tests of cognitive capacity and by testing cognitive function during IADL performance.

This protocol also addresses the need for pilot data to provide the empirical basis for future within-subject cross-over studies. The pilot data will inform the need to account for practice effects while estimating magnitude and duration of treatment effects from a single session of iTBS alone and a single session of iTBS + APT. As iTBS can now be tailored to each Veteran's unique neuropathology and because a single iTBS session can create a potentiated neural environment, iTBS is ideal to study alone. For healthy controls, one session of iTBS to the dorsal-lateral-prefrontal cortex (DLPFC), for example, induces gains in executive functioning. These immediate effects enhance feasibility of future cross-over studies explicating the constellation of Veteran-specific factors related to a Veteran's responses to multiple interventions. APT is ideal for pairing with iTBS, in part, because APT can be tailored to each Veteran's unique global and domain specific cognitive challenges. The tenets of metaplasticity also suggest that APT is ideal because APT is based on principles of exercise-dependent plasticity where novel training-exercises across five domains are provided to deliver stimuli of differing intensity. When APT is provided after iTBS, the provision of targeted APT stimuli during the time of iTBS enhanced plasticity is thought to regulate the plasticity ultimately optimizing cognitive gains as well as carry over of training-related gains.

Testing the scalability of an approach to feasibly and effectively tailor iTBS and APT for Veterans across stroke and TBI, advances rehabilitation research by enabling future research addressing the need for an empirical basis to tailor a broad range of cognitive rehabilitation strategies for Veterans across neurologic diagnoses. If the scientific basis for determining how-to feasibly and effectively tailor cognitive restoration interventions remain undeveloped, then Veterans with persisting cognitive impairments will continue to have diminished quality of life and sub-optimal function, ultimately relying on caregivers for performing daily activities.

Rehabilitation research capabilities for complex chronic populations will be advanced by leveraging the study team's collective expertise developing neuromodulatory interventions and developing methods to mitigate scientific barriers (e.g., imaging motion; neural targeting; differential diagnoses; detecting treatment responsiveness; study designs and complex analyses). As creating a scientific basis for feasible and effective development of precision Veteran-tailored cognitive restoration interventions has never been explored, the PI has not been funded in this area. [name] has, however, assembled an interdisciplinary team of experts with established collaborations to address this long-standing need.

